4 STUDY DESIGN

4.1 Overall Design

The purpose of this study is to evaluate the effect of ensifentrine on the proportion of patients hospitalized with COVID-19 infection with recovery over 29 days.

This is a single center, randomized, double-blind, parallel group, placebo-controlled study to determine the efficacy and safety of ensifentrine 2 mg BID administered via pMDI added on to SoC treatment for COVID-19 infection compared to subjects receiving SoC plus placebo.

Patients 18 to 80 years of age must be hospitalized with a confirmed diagnosis of SARS-CoV-2 infection confirmed by PCR test and displays at least one of the following: Respiratory rate greater than 24, new cough, new atypical chest pain, new dyspnea, oxygen saturation <97% at rest, chest x-ray with new changes consistent with COVID-19 related airspace disease.

Patients meeting criteria for inclusion and none of the criteria for exclusion at randomization will be randomized to receive study medication until to hospital discharge or up to 29 days of treatment, whichever comes first. Patients will be randomized 2:1 to receive one of the following study treatments:

- Treatment Arm 1 (n=30): Blinded ensifentrine (2 mg) pMDI BID + Standard of Care treatment for COVID-19 infection
- Treatment Arm 2 (n=15): Blinded placebo pMDI BID + Standard of Care treatment for COVID-19 infection

Randomized patients will receive blinded ensifentrine or placebo twice daily, approximately 12 hours apart in the morning and evening, through 29 days or until discharge from hospital, whichever is first. Patients will self-administer 4 actuations (puffs) pMDI observed by study staff at each dosing event.

During the treatment period, patients will undergo all assessments and procedures as outlined in the SoA until hospital discharge. Patients completing treatment will complete a study contact (telephone or visit as required) within 4 to 10 days of discharge or early withdrawal. All enrolled patients will complete a telephone contact 26 to 32 days and 55-65 days following receipt of 1st dose of study medication for assessment of clinical status via the ordinal scale, need for re-hospitalization and vital status.

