4.3 Justification for Design

This study is designed as a randomized, double-blind parallel group study evaluating impactful outcomes to patients, treating physicians, and healthcare facilities. As a small, unpowered pilot study, Verona Pharma aims to quickly collect data informing on the potential utility of inhaled ensifentrine pMDI in patients with COVID-19 by evaluation of trends across key independent endpoints.

The study is randomized 2:1 to ensifentrine:placebo in order to minimize the number of patients exposed to placebo during the study. A treatment duration of up to 29 days was selected to ensure that most hospitalized patients could receive study treatment during their full course of hospitalization, as the CDC has recently reported the median duration of hospitalization in patients who survived to be 10 to 13 days and median range of viral shedding among hospitalized patients to be 12–20 days (CDC Interim Clinical Guidance for Management of Patients with Confirmed Coronavirus Disease (COVID-19), June 2, 2020).

The patient population includes hospitalized patients with moderate to severe COVID-19, as we anticipate ensifentrine benefit including preventing progression to respiratory failure or other clinical conditions defined as Critical COVID-19 (FDA COVID-19: Developing Drugs and Biological Products for Treatment or Prevention Guidance for Industry).

Ensisfentrine has not shown evidence of liver injury in trials including over 1300 patients. Nonclinical data indicate that circulating ensifentrine is rapidly and extensively metabolized. At physiologically relevant concentrations (approximately 3 nM), metabolism is primarily mediated by cytochrome P-450 (CYP) 2C9 (93%); and to a lesser extent CYP2D6 (24%) and CYP3A4 (less than 5%). A drug-drug interaction study in healthy volunteers has shown that concomitant dosing of nebulized ensifentrine 3 mg with steady state fluconazole, an inhibitor of CYP2C9 and CYP3A4, resulted in an increase in C_{max} and AUC_{0-inf} of 41% and 63% when compared with ensifentrine alone (RPL554-PK-102; IBv19). This less than 2-fold increase is not considered clinically meaningful, as ensifentrine of up to 6 mg twice daily was found to be well tolerated with a comparable adverse event profile to placebo for over 4 weeks of dosing (Study RPL554-CO-203, IBv19). Because of this data, patients with some level of liver enzyme

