8.5 Post Discharge/Day 29 Contacts

Following Day 29 or discharge from the hospital (if earlier), there will be three points of contact with all study patients, regardless of hospitalization status. Each contact will require the completion of a Follow-up eCRF (**Table 15**).

- Discharge Contact: 4 to 10 days after discharge from hospital, if discharged within the 29-day treatment period.
 - If the patient remains hospitalized after Day 29, study treatment and data collection procedures still end on Day 29 (with the exception of contacts in this section) and contact with the patient will take place 4 to 10 days after receipt of last dose of study medication (Day 29).
- Day 29 Contact: 26 to 32 days after first dose of study medication. If the Discharge Contact and Day 29 Contact fall within same window, this contact will be combined to the Day 29.

- Day 60 Follow-up: 55 to 65 days after first dose of study medication.
 - Should a patient or their medical contact be unable to be contacted at any of these timepoints, a vital records search will be performed to determine the patient’s vital status approximately 60 days after first dose of study medication.

Table 15. Post-discharge follow-up activities.

Assessment	Information
Follow-up date	
 • Date of follow-up contact
Clinical status assessment (7-point ordinal scale)	
 • Assessed and documented, as above for Day 1 (clinical and vital status)
Re-hospitalization status or remains in hospital	
 • Any incidence of re-admission to the hospital following a 24-hour period of discharge (date and duration) that is related to COVID-19 • Date of discharge (if after Day 29) should be noted in the Follow-up eCRF.
Adverse Events assessments	
 • Documented, as above for Day 1

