8.6.1 Time period and frequency for collecting AE and SAE information

For this study, AEs and SAEs will be collected from the time of the first dose of study medication through the follow-up (end of study) visit.

SAEs assessed as related to study participation (e.g., study treatment, protocol-mandated procedures, invasive tests or change in existing therapy) will be collected from the time of consent through the follow-up visit.

All SAEs will be recorded and reported to the Sponsor or designee within 24 hours, as indicated in [Appendix 4](#). The Investigator will submit any updated SAE data to the Sponsor designee within 24 hours of it being available.

Investigators are not obligated to actively seek AE or SAE after conclusion of the study participation. However, if the Investigator learns of any SAE, including a death, at any time after a patient has been discharged from the study, and he/she considers the event to be reasonably related to the study medication or study participation, the Investigator must promptly notify the Sponsor.

The method of recording, evaluating, and assessing causality of AE and SAE and the procedures for completing and transmitting SAE reports are provided in [Appendix 4](#).

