9.5 Safety Analysis

Safety endpoints include SAEs and AEs (Protocol Appendix 4). Adverse events will be analyzed using quantitative and qualitative measures.

Treatment-emergent adverse events will be summarized by treatment group for all AEs, related AEs, serious adverse events, deaths, adverse events leading to discontinuation of study medication or to withdrawal from study, adverse events of different severity and adverse events of different chronicity.

Treatment-emergent adverse events will be coded using MedDRA and summarized by system organ class and preferred term for each treatment group.

The time to the composite AE endpoint (death, SAE, severe AE or ET/W of treatment during first 29 days) will be compared between treatment groups using the log-rank test and difference between treatment arms will be expressed as a difference in proportions as measured by the Cochran Mantel-Haenzel (stratum)-weighted estimator based on the fitted logistic regression model

• If '0' events, proportions will be presented.

Summaries of the results of the safety analysis are displayed in Table 12.

Table 12. Clinical study RPL554-COV-201 analysis tables - Safety Analyses.

Table #	Table Name
14.3.1	Time to first composite AE (Safety Analysis Set)
14.3.2	Number/Proportion Treatment emergent adverse events summary (Safety Analysis Set)
14.3.3	Number/Proportion TEAEs by system organ class and preferred term (Safety Analysis Set)
14.3.4	Number/Proportion TEAEs leading to discontinuation of study treatment by system organ class and preferred term (Safety Analysis Set)
14.3.5	Number/Proportion TEAEs causally related to the study treatment by system organ class and preferred term (Safety Analysis Set)
14.3.6	Number/Proportion TEAEs by maximum severity by system organ class and preferred term (Safety Analysis Set)
14.3.7	Number/Proportion Serious TEAEs by system organ class and preferred term (Safety Analysis Set)
14.3.8	Number/Proportion Serious TEAEs causally related to the study treatment by system organ class and preferred term (Safety Analysis Set)
14.3.9	Number/Proportion Serious TEAEs by maximum severity by system organ class and preferred term (Safety Analysis Set)
14.3.10	Number/Proportion Serious TEAEs leading to discontinuation of study treatment by system organ class and preferred term (Safety Analysis Set)
14.3.11	Number/Proportion TEAEs with an outcome of death by system organ class and preferred term (Safety Analysis Set)

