Table 14.1.11: COVID-19 Treatment and other Concomitant Respiratory Medications, ITT

Medications Introduced from initiation of study medication

		Enrolled (N=45)	Ensifentrine (N=30)	Placebo (N=15)
Taking COVID-19 Treatment	Yes			•
	No			
Antibiotics	Yes			
	No			
Antiviral Agent	Yes			
-	No			
Corticosteroid	Yes			
	No			
Intravenous Fluids	Yes			
	No			
Non-steroidal Anti-inflammatory	Yes			
	No			
other	Yes			
	No			

pg. 44 Confidential

Table 14.2.1: Study Medication Compliance from initiation of study medication

		Enrolled	Ensifentrine Placeb		
		(N=45)	(N=30)	(N=15)	
Missed dose of study medication after	Yes				
administration of 1 st	No*				

^{*}No means 100% compliance Listing will have information for doses missed

pg. 45 Confidential

Table 14.2.2: Patient last day receiving study medication from initiation of study medication, by study day

	Study Day	Enrolled (N=45)	Ensifentrin e (N=30)	Placebo (N=15)
Patient final day receiving study medication	2			
	3			
	4			
	5			
	6			
	7			
	8			
	9			
	10			
	11			

Study day of when the patient was administered their last dose of study medication (post-1st dose on Day 1).

pg. 46 Confidential

Table 14.2.3: Proportion of Patients with Recovery* from initiation of study medication at 29 Days, ITT

		Ensifentrine (N=30)	Placebo (N=15)
Proportion Recovered (scored 1 or 2) at Day 29 Overall Analysis results		N	Ň
Proportion recovered by: Age Group	< 65 years old	N (XX%)	N
	> 65 years	Ň	N
Gender	Male	N	N
	Female	N	N
Disease Severity	Moderate	N	N
Smoking History	Present	N	N
	Previous	N	N
	Never	N	N
# of Co- morbidities	None	N	N
	One	N	N
	Two or more	N	N

n = number of patients with recorded value

pg. 47 Confidential

^{*} Recovery = one of the following two categories from the 7-point ordinal scale:

^{1.} not hospitalized, no limitations of activities;

^{2.} not hospitalized, limitation of activities, home oxygen requirement, or both.

Table 14.2.4: Proportion of Patients with Recovery* from initiation of study medication at 29 Days, PP

		Enrolled (N=45)	Ensifentrine (N=30)	Placebo (N=15)
Overall				
Patient with Recovery	Yes No			

^{*} Recovery = one of the following two categories from the 7-point ordinal scale: 1. not hospitalized, no limitations of activities;

Confidential pg. 48

^{2.} not hospitalized, limitation of activities, home oxygen requirement, or both.

Table 14.2.5: Time to recovery*, from initiation of study medication - Day 29 (or discharge, whichever was first)

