TEAEs were defined as all AEs that started after the first dose of study treatment or started after the first dose of study treatment or started prior to first dose of study treatment and worsened, based on the Investigator's assessment of severity on or after the first dose of study treatment. TEAEs with a missing severity were classified as severe

pg. 64 Confidential

Table 14.3.3: Number/Proportion TEAEs by System Organ Class and Preferred Term

	Statistic	Total	Ensifentrine (N=30)	Placebo (N=15)
System Organ Class Preferred Term			(11 00)	(11 10)
Patients with at least one TEAE	N (%)			
Metabolism and nutrition disorders	N (%)			
Dehydration, hyperglycemia	N (%)			
Gastrointestinal disorders				
Diarrhoea				
Investigations	N (%)			
Alanine aminotransferase increased, Aspartate aminotransferase increased	N (%)			
Vascular disorders	N (%)			
Hypertension	N (%)			
Shock	N (%)			

n = number of patients

Table 14.3.4: Number/Proportion TEAEs Leading to Discontinuation of Study by System Organ Class and Preferred Term

Table 14.3.5: Number/Proportion TEAEs Causally Related to the Study Treatment by System Organ Class and Preferred Term

pg. 65 Confidential

Table 14.3.6: Number/Proportion TEAEs by Maximum Severity by System Organ Class and Preferred Term

System Organ Class	Severity	Statistic	Total	Ensifentrine (N=30)	Placebo (N=15)
Preferred Term Patients with at least one TEAE	Severe	N (%)			
	Moderate Mild	N (%) N (%)			
SOC	Severe				
	Moderate				
	Mild				
Preferred Term	Severe				
	Moderate				
	Mild				

Table 14.3.7: Number/Proportion Serious TEAEs by System Organ Class and Preferred Term

Table 14.3.8: Number/Proportion Serious TEAEs Causally Related to the Study Treatment by System Organ Class and Preferred Term

Table 14.3.9: Number/Proportion Serious TEAEs by Maximum Severity by System Organ Class and Preferred Term

Table 14.3.10: Number/Proportion Serious TEAEs Leading to Discontinuation of Study by System Organ Class and Preferred Term

Table 14.3.11: Number/Proportion Serious TEAEs with an Outcome of Death by System Organ Class and Preferred Term

Exploratory Analyses

ECMO: invasive mechanical ventilation or extracorporeal membrane oxygenation

Description of the distribution of the 7-point ordinal scale outcomes using plots (e.g., stacked bar plots representing the proportion of patients in each category, by treatment arm, over time).

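### The TEAE definition has a start but no end, so the general TEAE tables pool on-drug onsets with all onsets to Day 60; an on-/post-treatment split should sit beside them

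*SAP*

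**What the plan says.** - **Definition.** The footnote to shell Table 14.3.2 (SAP section 14) is the only place where TEAE is defined: "TEAEs were defined as all AEs that started after the first dose of study treatment", plus events already present that worsen after it. No closing date is given. Protocol 10.5 and SAP 9.5 use the term without defining it.
- **Collection.** Protocol 8.6.1: "AEs and SAEs will be collected from the time of the first dose of study medication through the follow-up (end of study) visit". The last contact is in Protocol 8.5: "Day 60 Follow-up: 55 to 65 days after first dose of study medication".
- **Dosing.** Protocol 4.1 gives study medication "through 29 days or until discharge from hospital, whichever is first". Shell Table 14.2.2 has the row label "Patient final day receiving study medication", with rows for study days 2 to 11 and no counts.
- **Tables.** SAP 9.5, Table 12 lists 14.3.2 to 14.3.11. None separates onsets on drug from onsets after the last dose. Percentages in 14.3.2 use every patient in the arm as denominator, without regard to exposure.
- **Composite AE.** SAP Table 5 follows it through hospitalization, Day 29 and Day 60. SAP 8.7 censors event-free completers at the Day 29 visit. SAP 9.5 limits it to the first 29 days.

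**The concern.** Safety and tolerability is a stated objective, and no formal safety board is planned; Protocol 11 has a team review blinded pooled AE data. The by-arm TEAE tables are therefore the main planned comparison of adverse events. Protocol Appendix 4 counts the expected progression, signs and symptoms of COVID-19 as AEs, so illness after discharge enters the same cells as events that began while the patient was inhaling the drug. That background is common to both arms. It pulls risk ratios toward 1 and makes an on-drug contrast harder to see.

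A second mechanism is ascertainment. AEs are assessed daily in hospital (Protocol 8.1 and 8.3) but only at the follow-up contacts afterwards (Protocol 8.5). Length of stay is itself an efficacy outcome (SAP 9.4.6). An arm discharged sooner is observed closely for fewer days, which can lower its crude TEAE percentage for reasons unrelated to tolerability.

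**Working it through.** The documents state no AE rate, detectable difference or power, so there is no figure of the plan's own to reproduce. The risks below are assumptions; the dates are from the documents.

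**1. Share of the window off drug** = (60 − days on drug) / 60, counting a last dose on Day *d* as *d* days on drug.

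| Source of time on drug | Days | Off drug |
|---|---|---|
| Maximum course (Protocol 4.1) | 29 | 31/60 = 52% |
| Cited stay (Protocol 4.3) | 13 to 10 | 47/60 = 78% to 50/60 = 83% |
| Shell 14.2.2 rows | 11 to 2 | 49/60 = 82% to 58/60 = 97% |

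The middle row uses Protocol 4.3: "median duration of hospitalization in patients who survived to be 10 to 13 days". Dosing starts after admission, so time on drug for such a stay would if anything be shorter. With the last contact at Day 55 or Day 65, the 29-day figure becomes 26/55 = 47% or 36/65 = 55%.

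**2. What pooling does to a contrast.** Let pT and pC be the on-drug-period risks and q the off-drug risk, taken as equal in both arms and independent of the first period. Pooled risk = 1 − (1 − p)(1 − q), so

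pooled risk difference = (1 − q)(pT − pC).

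The loss of absolute difference therefore depends on the background risk q, not directly on the share of days off drug. With assumed pT = 30% and pC = 10% (difference 20 points, ratio 3.0):

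| q | Pooled risks | Difference | Kept | Ratio |
|---|---|---|---|---|
| 5% | 33.5% v 14.5% | 19 points | 95% | 2.31 |
| 20% | 44% v 28% | 16 points | 80% | 1.57 |
| 40% | 58% v 46% | 12 points | 60% | 1.26 |
| 60% | 72% v 64% | 8 points | 40% | 1.13 |
| 80% | 86% v 82% | 4 points | 20% | 1.05 |

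At 30 v 15 patients, two-sided Fisher power for 30% v 10% is about 25% with no dilution and about 12% at q = 20%.

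**3. A milder assumed effect.** Take a 20% background risk over 60 days at constant hazard λ = −ln(0.8)/60, and a drug that doubles the rate while taken. Risk to Day 60 on drug = 1 − exp(−λ(60 + *d*)).

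- *d* = 5: 21.5% v 20.0%, ratio 1.07. On drug: 3.65% v 1.84%, an excess of 1.8 points, of which exp(−55λ) = 82% is kept.
- *d* = 11: 23.2% v 20.0%, ratio 1.16. On drug: 7.86% v 4.01%; exp(−49λ) = 83% of the excess is kept.
- If a fraction *f* = 25% or 50% of the background hazard falls on treatment, the ratio is [1 − 0.8^(1 + *f*)]/0.2 = 1.22 or 1.42, and 0.8^(1 − *f*) = 85% or 89% of the excess is kept.

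The ratio is hit hard; the absolute excess is not.

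**4. Which tables are exposed.** An event that starts after the last dose can hardly lead to stopping study drug, so 14.3.4 and 14.3.10, as titled in SAP Table 12, are barely affected. Tables 14.3.5 and 14.3.8 count only events judged related under blinding, a judgement that must weigh timing (Protocol Appendix 4). The fully exposed tables are 14.3.2, 14.3.3, 14.3.6, 14.3.7, 14.3.9 and 14.3.11.

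**The case against.** A reader might infer that every TEAE table pools a few days on drug with seven or eight weeks off, and that a drug-related excess is diluted almost out of sight. The documents do not support that.

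- **Size.** For uncommon terms (q of 5–20%), 80–95% of the absolute difference remains, and the tables show counts and percentages per arm. It nearly vanishes only if most patients would have an off-drug event anyway, which is plausible for the any-TEAE row at most. In the 5-day case above, the undiluted excess is 0.018 × 30 = about half a patient. Small numbers hide that under any window.
- **Exposure.** A few days on drug rests on shell rows without counts. A full course leaves 31 days, or 4.4 weeks, off drug.
- **Ascertainment.** Sparse detection after discharge also lowers q, so the two mechanisms partly offset each other.
- **Other outputs.** By-patient AE and dosing listings allow on-drug events to be rebuilt for 45 patients. Protocol 10.5 permits time-to-event plots for selected AEs, but as an option, and the SAP lists no such output beyond the composite.
- **The remedy has its own bias.** A window that closes at the last dose closes at discharge, or at stopping for deterioration (Protocol 7.1.1). Late complications in the sickest patients could then move to the post-treatment column. Day 60 gives both arms the same nominal follow-up.

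The last point stands: the on-treatment cut can only be supplementary. None of these points supplies an end to the TEAE window or a by-arm table of on-drug events.

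**Conclusion.** The concern holds as a moderate, cheaply corrected reporting weakness in an exploratory, unpowered pilot. The TEAE window is open-ended and in practice runs to Day 60, while at least about half of it (52% after 29 days of dosing, more with shorter stays) falls after the last dose. The consequence is a lowered risk ratio and a blurred on-drug contrast in the six general tables, with most of the absolute difference intact when off-drug background is low. The time shares follow from the documents. The ratios and power rest on assumed risks, on an off-drug risk equal between arms, and on independence of the two periods. The stated composite-AE windows also disagree with one another, and a 29-day window is not an on-treatment window for patients discharged earlier.

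**What to change.** 1. Keep all TEAE tables to Day 60 as the main comparison between arms.
2. In SAP 9.5 and the 14.3.2 footnote, state that the overall TEAE window ends at the Day 60 contact. Define an on-treatment period (first dose to last dose plus a lag that the sponsor sets before database lock) and a post-treatment period (from then to the last contact).
3. Produce 14.3.2, 14.3.3 and 14.3.7 by period and arm, with events per 100 patient-days in the period beside the percentages.
4. State in the SAP that time on drug is itself affected by outcome, so the on-treatment cut is supplementary and is read beside the Day 60 table. Patient-day rates help with unequal stays but do not remove this, because stopping is informative.
5. Reconcile the composite-AE window across SAP Table 5, 8.7 and 9.5. Align the titles of shells 14.3.4 and 14.3.10, which refer to discontinuing the study, with SAP Table 12, which refers to study treatment.

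Cost: SAP wording and extra cuts of three tables from AE onset and dosing dates already collected. The on-treatment cut will hold fewer events and give wide intervals.
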